6. STUDY SETTING

Adult patients will be recruited from Nottingham Audiology Service (NAS), Nottingham University Hospitals NHS Trust. Quantitative outcomes will be obtained by telephone, email or post. Qualitative assessments will take place at the NIHR Nottingham BRC.

7. SAMPLE AND RECRUITMENT

7.1. Eligibility Criteria

CONFIDENTIAL

Page 24 of 39

Ida Telecare

IRAS: 232078

Over 200 new patients attend initial hearing assessment appointments at NAS each month. Typical response rates for similar recruitment strategies at NAS has been at least 10 consenting patients per month (Ferguson et al. 2016).

All patients invited to direct referral hearing assessment appointments at NAS between September 2017 and February 2018 will be invited to take part in the study.

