Key Protocol Contributors	
[name] Details as above
 
[name] Details as above
 
[name] Otology and Hearing Group, Division of Clinical Neuroscience School of Medicine, University of Nottingham. NIHR Nottingham Biomedical Research Centre

Ida Telecare

IRAS: 232078

	
[name] [contact] [contact] [contact]
 
[name] The Ear Foundation [name] [contact] [contact]
 
[name] Nottingham University Hospitals NHS Trust NIHR Nottingham Biomedical Research Centre [name] [contact] [contact] [contact]
 
[name] Nottingham Audiology Service [name] [contact] [contact] [contact]

Committees	
Project Management Group
 
[name], details as above
 
[name], details as above
 
[name], details as above
 
[name], details as above
 
[name], details as above
 
[name], details as above

Ida Telecare

IRAS: 232078

STUDY SUMMARY

Study Title	Feasibility and effectiveness of Ida Telecare tools for NHS Audiology patients
Internal ref. no. (or short title)	Ida Telecare
Study Design	Feasibility study and RCT
Study Participants	Patients attending Nottingham Audiology Service
Planned Size of Sample (if applicable)	Feasibility study: N/A RCT: n=56 (28 per arm)
Follow up duration (if applicable)	N/A
Planned Study Period	16 th October 2017- 31 st August 2018

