5. STUDY DESIGN AND METHODS OF DATA COLLECTION AND DATA ANALYSIS

Study design: Two single-centre sub-studies assessing 1. Feasibility of implementing the Ida Telecare platform within an NHS adult audiology service, and 2. Effectiveness of the Ida Telecare tool '*Why Improve My Hearing?*', in a cohort of first-time NHS audiology patients. Both sub-studies will use mixed-methods (integrating quantitative and qualitative methodologies), which is considered advantageous in the evaluation of patient-centred care, providing an in-depth understanding of the patient experience (Agency for Healthcare Research and Quality 2013).

All patients invited to direct referral hearing assessment appointments at Nottingham Audiology Service between September 2017 and February 2018 will receive a study information pack alongside their appointment confirmation letter. The pack will contain a study invitation letter, the participant information sheet and a reply slip with a pre-paid addressed envelope for return. Upon receipt of completed reply slips, eligible patients will be randomised to one of the two intervention sub-studies (feasibility or effectiveness) using minimised allocation based on gender (male/female) and age: younger (<70 years old)/older (70 years old or greater). The minimised allocation will be generated and maintained by a researcher not directly involved in patient recruitment or testing (e.g. EH, [name]), using OxMaR software (O'Callaghan 2014). Patients will be contacted by a researcher (by telephone) to answer any questions they may have about the study. The researcher will then send an informed consent form for the patient to complete and return by email or post.

Recruitment will take place for a fixed duration of 6 months. If the recruitment target of n=56 patients for sub-study 2 has been reached before the end of the 6-month recruitment period, all subsequent patients returning reply slips will be automatically allocated to the feasibility study (sub-study 1).

Sub-study 1: Feasibility

1. *Implementation: Feasibility data and Think Aloud*

Patients enrolled on this sub-study arm will be sent links to each of the Ida telecare tools by the Research Assistant (RA) by email wherever possible (alternatively via post) and invited to use as many of the online tools as they wish at home, prior to each of their hearing appointments (assessment, fitting, optional follow-up). Patients will be asked to provide the researcher with a copy of

Ida Telecare

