7.3. Recruitment

7.3.1. Sample identification

All patients invited to direct referral hearing assessment appointments at NAS between beginning-September 2017 and end-February 2018 will be sent a study information pack alongside their appointment confirmation letter, by post (sent via NAS, with administrative assistance from a NIHR Nottingham BRC researcher). The pack will contain a study invitation letter, a participant information sheet, and a reply slip with a pre-paid addressed envelope for return. Half of the information packs will recruit patients to the Feasibility sub-study, and half to the Effectiveness sub-study. Only participants who return the reply slip stating that they are happy to take part in the study will be contacted by the research team. The research team will not access information stored in NHS patient records in this research, with the exception of hearing assessment results (Pure Tone Audiometric (PTA) thresholds) and hearing aid take-up rates, which are data required to fully describe the study sample.

For visits to the research unit, travel expenses will be reimbursed and participants will be offered a token payment of £5 per hour to, in part, recompense for their time.

Audiologists involved in seeing patients that have taken part in this research will be identified by the Nottingham Audiology Service administration team. All audiologists involved will all be invited by email to take part in semi-structured interviews. The email will provide the audiologist information sheet as an attachment. Those audiologists agreeing to take part in the interviews will be invited to attend the NIHR Nottingham Biomedical Research Unit where informed consent will be obtained.

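### At the protocol's only cited recruitment rate, a half-and-half split gives the RCT about 30 patients rather than 56, and the two descriptions of that split cannot both operate

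*Protocol*

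**What the plan says.** - **Rate and pool.** Section 7.1: "Over 200 new patients attend initial hearing assessment appointments at NAS each month", and "Typical response rates for similar recruitment strategies at NAS has been at least 10 consenting patients per month". No other recruitment rate appears in the protocol.
- **Window.** Section 5: "Recruitment will take place for a fixed duration of 6 months". Sections 5, 7.1, 7.2.2 and 7.3.1 date it from September 2017 to February 2018. The study summary gives the study period as "16 th October 2017- 31 st August 2018".
- **Assignment to sub-study, Section 5.** "eligible patients will be randomised to one of the two intervention sub-studies (feasibility or effectiveness) using minimised allocation", using gender and age, once the reply slip is back. No ratio is stated.
- **Assignment to sub-study, Section 7.3.1.** "Half of the information packs will recruit patients to the Feasibility sub-study, and half to the Effectiveness sub-study".
- **Contingency, Section 5.** The rule opens "If the recruitment target of n=56 patients for sub-study 2 has been reached before the end of the 6-month recruitment period" and then sends all later responders to feasibility. There is no rule for the opposite case.
- **Target, Section 7.2.1.** The RCT needs 50 evaluable patients (25 per arm) for a 10-point MARS-HA difference at 80% power, raised to 56 (28 per arm) for 15% attrition. The SD comes from a cited study and is not given. The quantitative size of the feasibility sub-study is stated as not applicable.

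**The concern.** The RCT's size and power are presented as what the trial will deliver, but the rate, window and split that the protocol states do not produce them. A reader of Section 7.2.1 alone would expect 80% power. A reader who multiplies through Sections 5, 7.1 and 7.3.1 would expect roughly an even chance of detecting the target difference.

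The allocation text is a separate practical problem. If the posted pack decides the sub-study, there is nothing left to minimise on the responder's age and gender. If minimisation after the reply decides it, no pack can belong to one sub-study. Staff cannot follow both sections.

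**Working it through.** **1. The plan's own figure.** Without an SD, 25 per arm cannot be reproduced independently. It can be inverted (10 points, two-sided 5%, 80% power, equal arms):
- Normal approximation: SD = 10 / [(1.960 + 0.842) × √(2/25)] ≈ 12.6.
- t-test (noncentral t): SD ≈ 12.4.

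These values are assumptions carried into step 4. For the step from 50 to 56, 25 × 1.15 = 28.75, which gives 28 if rounded down. This does not affect the recruitment question.

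**2. Yield at the cited rate.**
- Both sub-studies: 10 per month × 6 months = 60 consents.
- RCT at an equal split: 60 × 0.5 = 30, or 15 per arm.
- Against target: 30/56 = 54%, a shortfall of 26.

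This takes half the packs to mean half the consents, so it assumes similar response to both kinds of pack.

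**3. What 56 would need at an equal split.**
- Consents: 56/0.5 = 112.
- Rate: 112/6 ≈ 18.7 per month.
- Share of 1,200 attenders (200 × 6): 112/1,200 ≈ 9.3%, against 60/1,200 = 5% at 10 per month.
- Time at 10 per month: 112/10 = 11.2 months.

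| Consents per month | Total in 6 months | RCT at equal split |
|---|---|---|
| 10 | 60 | 30 |
| 12 | 72 | 36 |
| 15 | 90 | 45 |
| 18.7 | 112 | 56 |
| 20 | 120 | 60 |

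If recruitment is Poisson, the chance of at least 56 RCT patients is about 0.001% at 10 per month and about 6% at 15 per month.

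**4. Power for a 10-point difference.** Noncentrality = 10 / [SD × √(2/n)], with n per arm.

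| Recruited | Attrition | n per arm | Power, t-test (SD 12.4) | Power, normal (SD 12.6) |
|---|---|---|---|---|
| 56 | none | 28 | 84% | 84% |
| 56 | 15% | 23.8 | 78% | 78% |
| 30 | none | 15 | 57% | 58% |
| 30 | 15% | 12.75 | 50% | 52% |

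**5. The two assignment rules side by side.**

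| | Section 5 | Section 7.3.1 |
|---|---|---|
| When the sub-study is set | After the reply slip | When the pack is posted |
| How | Minimisation on gender and age | By type of pack |
| Ratio | Not stated | Half and half, of packs |
| Redirecting later responders once 56 is reached | Works as written | Moves people who answered an RCT pack |

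**The case against.** The strongest reply is that the rate is a minimum. Actual recruitment could be higher, the equal split is explicit only for packs, and Section 5 gives no ratio. All of that stands, and it means 30 is not a forecast. It does not close the gap: 56 needs nearly double the only rate cited, and nothing in the protocol supports that. Even all 60 consents would barely cover 56, and neither section sends nearly everyone to the RCT.

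It is also fair that a shortfall costs precision and does not bias the comparison between arms. The Rationale and Section 4.2 call the RCT an initial assessment giving preliminary evidence, and measuring recruitment is itself an objective. This lowers the severity.

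A reader might infer three stronger points that the protocol does not support:
- **That the 16 October start cuts recruitment to about 4.5 months.** Section 5 fixes six months, Sections 5, 7.1, 7.2.2 and 7.3.1 date it from September to February, and the timeline marks six recruitment months. Only the summary differs. This is a date inconsistency and not a shorter window.
- **That weighting allocation 2:1 or 4:1 towards the RCT solves the problem.** Section 5 wants 15 feasibility patients for goal-setting, all eligible for fitting, and a different 6 to 8 for Think Aloud: 21 to 23 people. At 60 consents, 2:1 leaves 20 and 4:1 leaves 12. Since 56 + 21 = 77 exceeds 60, no ratio serves both sub-studies at the floor rate.
- **That the redirection rule is a further defect in itself.** It acts on returned slips and works under Section 5. It misfires only under the pack version, so it is part of the same contradiction.

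**Conclusion.** The point holds and should be fixed. At the cited floor rate, over six months and with an equal split, the RCT receives about 30 patients, 54% of its target. Power for the 10-point difference is then about 57% with no attrition and about 50% with 15% attrition (58% and 52% by the normal approximation), against a planned 80%.

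The yield rests on a rate of exactly 10 per month and on the Section 7.3.1 split applying to consents. The power figures also rest on an SD back-solved from the plan's own sample size, since none is stated. The only contingency protects the feasibility sub-study's intake, and nothing provides for an RCT shortfall.

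The conflict between Sections 5 and 7.3.1 depends on none of these assumptions and needs correcting whatever the recruitment rate.

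**What to change.** - **Sections 5 and 7.3.1.** Keep one mechanism: generic packs, with the sub-study assigned after the reply slip as Section 5 describes. Delete the Section 7.3.1 sentence that divides the packs. State the ratio between sub-studies.
- **Section 7.2.1.** State the SD used, the consent rate needed for 56 under the stated ratio (about 18.7 per month if equal), and the expected RCT size and power at 10 per month.
- **If the ratio is weighted towards the RCT.** Show that it leaves enough patients for the 15 goal-setting and the separate 6 to 8 Think Aloud participants. That is a choice between the aims of the two sub-studies, and this review prescribes no ratio.
- **Dates.** Reconcile the October study start in the summary with the September recruitment start.

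The cost is protocol wording and a less favourable stated power.

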7.1.1. Inclusion criteria

- Adults aged ≥ 18 years (no upper age limit)
- Ability to offer informed consent
- Fluent in the English language (written and spoken, does not have to be their first language)
- Access to the Internet.

7.1.2. Exclusion criteria

- Previously prescribed hearing aids

7.2. Sampling

7.2.1. Size of sample

Sub-study 1: Feasibility

- Quantitative: Not applicable

One of the main aims of this Arm is to identify recruitment rates/intervention take-up in this population.

- Qualitative:
 - Think Aloud n=6-8 patients

Data collection will cease once data saturation has been reached. A sample size of 6-8 has been found to be generally sufficient to achieve data saturation for Think Aloud techniques (Henshaw et al. 2017).

- Semi-structured interviews with patients and audiologists: $n \leq 15$

Data collection will cease once data saturation has been reached (Guest et al. 2006).

Sub-study 2: Effectiveness

- Quantitative: n=56 participants (n=28 per arm)

In order to detect a 10% change in MARS-HA (smallest possible change) at a power of 80% and type II error rate of 5%, a total of 50 participants are required, 25 in each arm. This was calculated using a standard deviation for global MARS-HA scores derived from (Ferguson et al. 2016). As outcome measures will be taken immediately post-assessment, it is expected that fewer than usual participants will fail to complete outcome measures. Hence, a conservative attrition rate of 15% has been used, thus accounting for attrition, a total of 56 participants (28 per arm) will be recruited.

Ida Telecare

IRAS: 232078

- Qualitative: Semi-structured interviews with patients and audiologists

Data collection will cease once data saturation has been reached.

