Continuous data (e.g. age) will be summarised using means and standard deviations, whereas categorical data (e.g. gender) will be summarised using percentages. Medians and quartiles will be reported for non-parametric data, and means, standard deviations and 95% confidence intervals for normally-distributed parametric data. Normality of continuous data will be assessed using histogram plots and the Shapiro Wilk Test. For each measure, the difference between arms will be examined

Ida Telecare

IRAS: 232078

using parametric (e.g. T-test) or non-parametric (e.g. Wilcoxon Rank Sum Test) statistics where appropriate. For categorical data, Chi-square test will be used, and Fishers exact test if any of the cells are less than 5. Statistical significance will be set at $p=0.05$ and corrected (e.g. Bonferroni) for multiple comparisons. As outcome data will be collected after the intervention period, no interim analyses will be performed.

2. *Patient and Audiologist views and experiences*

For the alternative pathway only:

A sub-set (6/28) of hearing assessment appointments will be video recorded to enable a detailed assessment of how the tools were jointly used by the patient and audiologist. The videos will also be shared with the research funders to identify how the tools might be improved or amended to better suit patients' needs in future.

A sample of patients and audiologists will be recruited from the alternative pathway using maximum variation sampling (Patton 1990), to take part in semi-structured interviews with a member of the research team. Interviews will examine patients and audiologists perceptions and experiences of using the 'Why Improve My Hearing?' telecare tool, specifically:

- what influenced patients use of the tool
- how, when and where the tool was used by patients in preparation for their hearing assessment appointment
- how the tool was used jointly by audiologists and patients within the clinical appointment
- what benefit(s) patients and audiologists attributed to use of the tool

The interview schedules will be designed to provide an in-depth understanding, and will be reviewed by patient representatives to ensure clarity of concepts and relevance to patients. Data collection will cease once data saturation has been reached.

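### Protocol 7.2.1: 56 recruits cover about 10% attrition, not the stated 15%, and 80% power is paired with a 5% type II error

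*Protocol*

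**What the plan says.** The size of the effectiveness sub-study is justified in one paragraph, Protocol section 7.2.1.

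- **Target difference:** "In order to detect a 10% change in MARS-HA (smallest possible change", in parentheses.
- **Error rates and evaluable sample:** "at a power of 80% and type II error rate of 5%, a total of 50 participants are required, 25 in each arm".
- **Variability:** "This was calculated using a standard deviation for global MARS-HA scores derived from" a cited earlier study. The SD itself is not printed.
- **Attrition and recruitment:** "a conservative attrition rate of 15% has been used, thus accounting for attrition, a total of 56 participants (28 per arm) will be recruited".

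The Study Summary repeats the total ("RCT: n=56 (28 per arm"). Section 5 uses 56 as the recruitment target: once it is reached, later responders go to the feasibility sub-study. The sample-size paragraph gives no type I error. The only significance level is in the analysis text of section 5: "Statistical significance will be set at $p=0.05$ and corrected (e.g. Bonferroni) for multiple comparisons". Sidedness is not stated; section 5 says only that "the difference between arms will be examined".

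**The concern.** The paragraph gives a required number, an attrition rate and a recruitment number, and the three do not fit together. At the stated attrition the trial ends with fewer completers than it says it needs. Because recruitment to this sub-study stops at 56, nothing later in the plan makes up the difference.

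The stated power and the stated type II error are two descriptions of the same quantity, and they disagree.

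The description of the target difference as the smallest possible change does not match the score that the calculation uses.

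This is the only quantitative justification for the trial's size, and a trial report would be expected to repeat it. At stake is whether the stated power, attrition allowance and error rates can be relied on as written.

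**Working it through.** **Inputs (Protocol 7.2.1 unless noted).** Required evaluable: 50 (25 per arm). Attrition: 15%. Recruited: 56 (28 per arm). Power: 80%. Type II error as stated: 5%. Difference: 10%, taken here as 10 points on the 0–100% scale (assumption). Significance level: 0.05 (section 5). SD: not printed. Sidedness: not stated.

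**1. Attempt to reproduce 56 from 50.**

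- Standard inflation, N/(1 − d): 50/0.85 = 58.8, so 59. By arm, 25/0.85 = 29.4, so 30 per arm and 60 in total.
- The common shortcut, N × (1 + d): 50 × 1.15 = 57.5, so 58. By arm, 25 × 1.15 = 28.75, so 29.
- Standard inflation at 10%: 50/0.90 = 55.6, so 56. By arm, 25/0.90 = 27.8, so 28.

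Neither method gives 56 at 15%. The standard method gives 56, and 28 per arm, at 10%.

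**2. Forward check.**

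- Completers: 56 × 0.85 = 47.6 (23.8 per arm), which is 2.4 short of 50.
- Largest loss that still leaves 50: 1 − 50/56 = 10.7%.

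**3. Effect on power.** Suppose 25 per arm gives exactly 80% power at a two-sided 5% level. The standardised signal scales with √n, so the unprinted SD is not needed. In the normal approximation, 1.960 + 0.842 = 2.802 at 25 per arm. At 23.8 per arm this becomes 2.802 × √(23.8/25) = 2.734, and 2.734 − 1.960 = 0.774, a power of 78.0%. The two-sample t-test gives the same:

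| Completers per arm | Power, two-sided | Power, one-sided |
|---|---|---|
| 25 | 80.0% | 80.0% |
| 24 | 78.3% | 78.5% |
| 23.8 | 78.0% | 78.2% |
| 23 | 76.5% | 76.9% |

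**4. Error rates.** Power = 1 − type II error. Power of 80% gives a type II error of 20%; a type II error of 5% gives power of 95%. Both figures cannot hold.

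**5. The target difference.** Section 5 describes MARS-HA as having four subscales, with responses on an 11-point scale from 0% to 100%. One step is 100/10 = 10 points on one item. Section 7.2.1 sizes the trial on the global score. A score that combines items over four subscales can change by less than one step of one item. The item count and the global scoring rule are not given, so how much less cannot be stated.

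**6. What 25 per arm implies about the SD (assumption only).** Solving the two-sample t-test for a 10-point difference:

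| Assumed test | Standardised difference | Implied SD |
|---|---|---|
| Two-sided 5%, 80% power | 0.81 | 12.4 |
| One-sided 5%, 80% power | 0.71 | 14.0 |

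The 50 itself can be neither confirmed nor refuted without the SD.

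**The case against.** The strongest reply is about size. The shortfall is 2.4 completers and about 2 points of power. No eligibility rule, allocation, endpoint or analysis changes. The protocol presents this sub-study as an initial assessment (section 2) yielding preliminary evidence (section 4.2). A reader can also recover the likely meaning of the 5%, because 80% power is stated in the same phrase and section 5 sets 0.05. All of this stands. It limits the seriousness of the point, but it does not make the figures agree.

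Four stronger readings are tempting, and the document does not support them.

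- **That the trial should have been sized for 95% power.** This takes the 5% literally and ignores the explicit 80%. A slip of label is far more likely.
- **That the 5% must be a two-sided type I error.** Type I is the most likely meaning, but section 7.2.1 does not say so and sidedness appears nowhere.
- **That the required 50 is wrong, or that the target is established as a very large effect.** The SD is not printed. Any standardised difference is back-calculated and moves with the assumed test.
- **That a null result would be read as excluding any change.** No such rule is stated, and section 5 commits to 95% confidence intervals for normally distributed data.

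The Study Summary entry is not a separate error. It agrees with section 7.2.1 and stays correct if 56 is kept.

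**Conclusion.** The point holds as two errors in section 7.2.1 and one minor wording fault.

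1. **Attrition.** The stated 15% was not carried into the 56. At 15%, about 47 participants complete instead of 50, and power is about 78% instead of 80%. This assumes that 25 per arm gives exactly 80% power and that losses are equal between arms. The power figure barely depends on sidedness (78.0% or 78.2%).
2. **Error rates.** The stated type II error contradicts the stated power. This needs no assumption.
3. **Minor.** The smallest-change label is unsupported for a global score.

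The paragraph should be corrected because its figures are wrong as written. The practical effect is small, and the design is not undermined.

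**What to change.** Amend the wording of section 7.2.1 and keep 56.

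- **Attrition:** either state that 56 allows for about 10% attrition, or keep 15% and state that about 47 completers are expected, with about 78% power. For reference, holding both 15% and 50 completers would take 60 recruits in equal arms.
- **Error rates:** replace the type II figure with the type I error actually used and its sidedness. The type II error that goes with 80% power is 20%.
- **Target difference:** delete the smallest-change label, print the SD taken from the cited study, and express the 10 points relative to that SD. The implied SDs in the working are assumptions and should not be copied into the protocol.

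**Cost:** a wording amendment. No extra patients are needed, and the analysis does not change. The stated attrition allowance or power becomes slightly less favourable.

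### A 15% attrition allowance on 50 required participants does not give 56: it needs 59 (60 with equal arms), and 56 covers only 6 losses (10.7%). A minor arithmetic correction.

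*Protocol*

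**What the plan says.** Section 7.2.1 of the Protocol sizes the RCT on a 10% change in the global MARS-HA score at 80% power and concludes that "a total of 50 participants are required, 25 in each arm". It expects less loss than usual because outcomes are taken straight after the assessment appointment. It then says that "a conservative attrition rate of 15% has been used, thus accounting for attrition, a total of 56 participants (28 per arm) will be recruited".

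The same target appears elsewhere:
- The Study Summary gives "RCT: n=56 (28 per arm".
- Section 5 uses it as a stopping point for RCT entry. The sentence that begins "If the recruitment target of n=56 patients for sub-study 2 has been reached before the end of the 6-month recruitment period" goes on to send all later responders to the feasibility sub-study.
- Section 5, Sub-study 2, part 2 describes the video-recorded appointments as 6 out of an arm of 28.

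The protocol gives no other attrition rate, inflation formula or rounding rule.

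**The concern.** An attrition allowance should leave the required number once the stated fraction has been lost. Here the required number, the loss rate and the recruitment total stand together in one paragraph, and a single division shows that they disagree. Either the rate or the total is misstated, and a reader cannot tell which.

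At stake is whether the sizing statement can be trusted at the loss rate it claims to absorb. The figure also has an operational role, because section 5 closes RCT entry at 56.

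**Working it through.** **Inputs (Protocol section 7.2.1):** required for analysis N = 50 (25 per arm); attrition d = 0.15; recruited 56 (28 per arm).

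**1. Trying to reproduce 56**
- Standard inflation, N/(1 − d): 50/0.85 = 58.8, so 59. Per arm, 25/0.85 = 29.4, so 30, or 60 in total. This does not give 56.
- Adding 15%, N × (1 + d), a common but incorrect method: 50 × 1.15 = 57.5, so 58. Per arm, 25 × 1.15 = 28.75, so 29, or 58 in total. This does not give 56 either.
- Adding 15% per arm and rounding down: 28.75 becomes 28, or 56 in total. This gives 56, but by a method that does not preserve 50.
- A 10% allowance: 50/0.90 = 55.6, so 56. This gives 56, but at a rate the protocol does not state.

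The source of 56 is therefore either a formula and rounding slip or a different rate. The document does not say which.

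**2. What 56 covers**
- Losses tolerated: 56 − 50 = 6, and 6/56 = 10.7%.
- Rounding this up to 11% would be slightly wrong: 56 × 0.89 = 49.84, just under 50.

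**3. What remains at 15% loss**
- 56 × 0.85 = 47.6 in total, or 28 × 0.85 = 23.8 per arm. In whole people that is 47 to 48.
- Shortfall in recruits: 59 − 56 = 3, or 60 − 56 = 4 with equal arms.

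**4. Effect on power (conditional)**

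Steps 1 to 3 need only 50, 15% and 56. Power needs more than the protocol prints. The standard deviation is taken from a cited study and not given, the sidedness is not stated, and the 5% is labelled as a type II rate. I assume a two-sided 5% two-sample t-test, a 10-point difference, and that 25 per arm is the smallest size reaching 80%. With the noncentral t distribution:
- 25 per arm gives exactly 80% at a standardised difference of 0.809, so SD = 10/0.809 = 12.4. This is the largest SD compatible with 25 per arm.
- 24 per arm would give exactly 80% at SD 12.1, so the SD must be above 12.1 for 25 to be the minimum.
- At 23.8 per arm, power is 78.0% at SD 12.4 and 79.7% at SD 12.1.
- At SD 12.4, the difference detectable with 80% power at 23.8 per arm is 10.3 points rather than 10.

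A one-sided 5% test, with 25 per arm giving exactly 80%, gives 78.2% at 23.8 per arm, so the choice of sidedness hardly matters here.

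**The case against.** **The effect is trivial.** The shortfall is 3 to 4 people and 0.3 to 2.0 percentage points of power, in a study the protocol presents as an initial assessment giving preliminary evidence. This stands, and it is why the point is minor. It does not make the sentence true.

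**The origin is an ordinary slip.** Adding 15% per arm and truncating gives exactly 28. That is plausible, but it explains the number without rescuing it: 50 are still not retained at 15% loss.

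**The cap at 56 may never bind.** Section 7.1 cites at least 10 consenting patients a month. Over 6 months that is about 60, and an even split between the two sub-studies would put about 30 into the RCT. The rate is a floor, so 56 may be reached, but on the only rate given the choice between 56 and 60 would not be the limiting factor. This also stands. The entry rule repeats the wrong figure, but the documents do not show that it will cost the trial patients.

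**Stronger readings.** A reader might infer that the sizing argument collapses or that the RCT is seriously underpowered. The figures do not support that: under the assumptions above, power at the stated loss stays between 78.0% and 79.7%. A reader might also want to write 78% into the protocol as a fact. The documents do not support that either. It is the unfavourable end of a range derived from a back-solved SD and an assumed sidedness. Section 5 also says that the significance level will be corrected for multiple comparisons. If that applied to MARS-HA, power would be lower for a reason unrelated to attrition. For illustration, halving alpha gives about 68 to 70% at 23.8 per arm, and about 71 to 73% even at the full 25.

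**Conclusion.** Wrong as written, and minor. The required 50, the 15% allowance and the target of 56 cannot all hold. At 15% the target should be 59, or 60 with equal arms. The present target covers 6 losses (10.7%), and a 15% loss leaves about 47 to 48. This conclusion uses only the protocol's own figures.

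The consequence for power, about 78 to 80% instead of at least 80%, depends on the assumptions in step 4 and should be treated as indicative. Whether 15% is a realistic loss rate is a separate question that this check does not address.

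**What to change.** **Preferred: keep 56 and correct the paragraph in section 7.2.1.** It could read: *Recruiting 56 (28 per arm) allows for 6 losses (10.7%); at 15% attrition about 47–48 would be analysed, slightly below the 50 needed for 80% power.* The sponsor should compute the exact power at that number from its own SD and alpha, and state both. No unconditional power figure should be taken from this review. The cost is one sentence and one recalculation, with no extra patients and no change elsewhere.

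**Alternative: keep the 15% allowance and change the total to 60 (30 per arm).** The change must be made in the Study Summary, in the recruitment target in section 5 and in section 7.2.1. The 6-out-of-28 description of the video-recorded appointments in section 5 must be changed to match, or a new inconsistency is left behind. The cost is 4 more participants and edits in those places.
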